### 4.2 Gender/Minority/Pediatric Inclusion for Research

Given that CityLife Neighborhood Clinic is located in a diverse neighborhood and has a diverse patient population, we expect that a large proportion of the study population will be African American and Hispanic males. Women are not eligible to participate in the study as they are not at risk for PCA. Children are excluded from participating, as their risk of PCA is non-existent.

### **4.3 Strategies for Recruitment and Retention**

### **4.4 Participant Withdrawal**

#### **4.4.1 Reasons for Withdrawal**

Participants are free to withdraw from participation in the study at any time upon request.

An investigator may terminate a study participant's participation in the study if:

- Any clinical adverse event (AE), laboratory abnormality, or other medical condition or situation occurs such that continued participation in the study would not be in the best interest of the participant.
- The participant meets an exclusion criterion (either newly developed or not previously recognized) that precludes further study participation.

### **4.5 Premature Termination or Suspension of Study**

This study may be suspended or prematurely terminated if there is sufficient reasonable cause. Written notification, documenting the reason for study suspension or termination, will be provided by the suspending or terminating party. If the study is prematurely terminated or suspended, the principal investigator will promptly inform the IRB and will provide the reason(s) for the termination or suspension.

Circumstances that may warrant termination include, but are not limited to:

- Determination of unexpected, significant, or unacceptable risk to participants.
- Insufficient adherence to protocol requirements.
- Data that is not sufficiently complete and/or evaluable.
- Determination of futility.

## **5 Study Intervention**

## 5.1 Study Behavioral or Social Intervention(s) Description

The goal of Aim 1 is to conduct 2 focus groups to identify gaps in awareness, cultural beliefs, and barriers to considering genetic counseling and genetic testing for PCA. Key themes identified during the focus groups will inform the development of the behavioral intervention in Aim 2. The goal of Aim 3 is to evaluate the impact of the intervention, focusing on outcomes related to decisional conflict about genetic testing and knowledge of PCA.

## 6 Study Procedures and Evaluations

### Aim 1: Focus Groups

We will conduct two focus groups of approximately 8 AA men each, recruited from the patient population at CityLife Clinic or the surrounding neighborhood. MEE Productions, Inc. will coordinate and moderate both of the focus groups. MEE Productions, Inc. is a nationally recognized communications, market research and social-marketing firm with roots in Philadelphia that specializes in developing cost-effective, cutting-edge and culturally relevant messages for hard-to-reach, low-income and underserved audiences. The study team has significant experience in working with MEE Productions, Inc. on a prior research study [DOD Synergistic IDEA Award (#PC140667)]. The goal of the focus groups will be to gather information on awareness, understanding, attitudes, and challenges to considering genetic testing for PCA. Factors such as knowledge of family cancer history, relevance of genetic testing in health, and competing risks and pressures will also be explored.

Prior to the start of each focus group, each participant will provide informed consent. Focus group discussions will be audio recorded and transcribed by a professional transcription company. The transcriptions will be verified for accuracy by a member of the research team who attended each focus group. Transcripts will be analyzed by iterative rounds of coding by at least two members of the research team, where specific themes and trends will be identified within each transcript and discussed by the research team until final consensus is reached. Themes will be identified as topics that consistently occur across transcripts, as well as similarities and differences between transcripts. NVivo software will be used to perform thematic content analysis. Participants will be compensated \$25 for attending a focus group.

### Aim 2/3: Behavioral Intervention

**Recruitment and training of peer health educators.** The study team has built strong AA community relationships from work on a prior funded DOD grant [Synergistic IDEA Award (#PC140667)]. Peer educators from this prior grant will be re-contacted to participate in the Peer Genetic Study. A total of five peer educators will be recruited. If prior peer educators are not available to commit to the study, additional avenues to recruit peer health educators will be through CityLife Clinics or MEE Productions, Inc. Men need not have previous health care experience to be trained as a peer educator. [name] or [name] will lead the educator training sessions. Culturally relevant issues will be addressed throughout the 9 training sessions, as they pertain to each of the training modules. Questions and concerns from peer health educators will also be addressed throughout the training. Peer educators will also complete human subjects training to be able to collect participant subject data during the intervention. Peer educators will attend training sessions in person, typically over the dinner meal, and will be compensated \$20/hour of training time.

**Development of genetic training materials.** Content of the training materials for peer educators will be adapted from ASCO's Practice Guideline Genetics Toolkit. The toolkit modules will be adapted as follows: (1) understanding hereditary cancer, (2) assessing hereditary cancer risk, (3) considerations of genetic testing and results, (4) management PCA and PCA screening based on genetic test results, (5) financial and ethical considerations of genetic testing, (6) cultural issues to address regarding genetic testing among AA males, (7) PCA risk and lifestyle modifications, (8) implications of genetic testing on family members, and (9) case scenarios. Based on input from the study team, MEE Productions, Inc. will develop print materials for the training sessions covering the aforementioned content.

**Assessment of competency.** To assess peer educator competency prior to the start of the intervention, we will adapt evaluation materials from the International Society of Nurses in Genetics 2011 Consensus Panel and survey on knowledge and understanding of PCA genetics and genetic results. Example true/false assessment questions will include: (1) Factors such as personal behavior (diet, exercise) and environmental conditions (exposures) can raise the risk of getting prostate cancer; (2) Men with a family history of prostate cancer should also consider other factors that could raise the risk of getting prostate cancer, such as diet or exposures; (3) A family history of prostate cancer can raise the risk of getting prostate cancer; (4) Family history of additional cancers, such as breast cancer, can raise the risk of getting prostate cancer; (5) Having a history of prostate cancer on his mother's side of the family, can raise the risk of a man getting prostate cancer; (6) A genetic test can tell if someone will definitely get prostate cancer in the future; (7) Genetic testing may still be important even if a man has prostate cancer; (8) Patients with one cancer can be at risk for getting other cancers if the patient has a genetic mutation.

Additional multiple-choice questions will include: (1) What types of genetic test results can you get from genetic testing? (2) How can genetic testing be used in treatment of prostate

cancer? (3) How can genetic testing be used in prostate cancer screening discussions? (4) What should a man know about genetic discrimination laws before proceeding with genetic testing? (5) What additional cancer risks might be learned from genetic testing for prostate cancer? Peer health educators will be expected to score correctly on 80% or more of the questions to proceed with the intervention in Aim 3. Any areas of deficiency in understanding will be addressed by the study team in a group format or one-on-one with a peer health educator.

**Participant Recruitment and Study Enrollment.** MEE Productions, Inc. will develop culturally-tailored recruitment materials including flyers, posters and email blasts for CityLife Clinics to send to their AA male patients. The goal is to enroll 176 men in the study. We are anticipating a roughly 15% attrition rate over the course of the intervention, producing a final sample size for analysis of 150 men. We anticipate, based on our previous experience in community-based research, that we will have to screen about 10 times that number, or about 2000 men, to reach our study recruitment goal of 176 men. The research team will work with CityLife Clinic to mail a study recruitment letter to eligible males at their clinic, inviting them to participate. A toll-free, local telephone number will be included in the letter for men to opt-out of the study. After two weeks, any male who has not opted out will receive a telephone call from a member of the research team to screen for study eligibility. We will supplement our recruitment at CityLife Clinic by grassroots outreach in the neighborhood surrounding the clinic, to invite men not associated with the clinic to participate. We will promote the study at community recreation centers, public libraries, housing complexes and apartments, local non-profit organizations, barbershops, and employment agencies. Men who see the flyers or a member of the study team in the community can also call the toll-free, local number to screen for eligibility and participate. This is a similar approach that the study team was successful in using for the previously funded DOD study.

**Study eligibility.** Men who call the telephone number associated with the study or are who approached in the community will be screened for eligibility by the study research manager. Any AA male with or without prostate cancer between the ages of 35-69 will be eligible for the study. Men must speak and read English comfortably, as all study materials will be in English. Men do not need to be established patients at CityLife Clinics to participate.

**Study Randomization and Informed Consent.** Those who are eligible to participate will be randomized to either the intervention or the control arm. Men randomized to the intervention arm will be scheduled to attend a health education session hosted at CityLife Clinic or virtually, while men who are randomized to the control arm will receive educational materials about PCA genetic testing in the mail or in person. All men who agree to participate will be read a consent statement over the phone or in person and will verbally agree to consent to participate. A copy of the consent statement will be provided to them for their records.

**Baseline Survey.** All participants will complete a brief baseline questionnaire over the telephone or in person with the study manager. Items to be assessed at baseline include knowledge about prostate cancer, their personal family cancer history, knowledge of genetic testing and screening, attitudes towards genetic testing, subjective norms about genetic testing, decisional conflict about genetic testing, and intentions to seek genetic counseling. Knowledge about PCA genetics and genetic testing will be measured using a 14-item scale, recently published by the study team in a population of men undergoing genetic testing. The measure for decisional conflict will be the SURE Decisional Conflict Scale, a low-literacy validated measure to screen for decisional conflict. The four questions encompass the following with Yes/No responses: (1) Do you feel sure about the best choice for you? (2) Do you know the benefits and risks of your options? (3) Are you clear about which benefits and risks matter most to you? (4) Do you have enough support and advice to make a choice? Demographic data related to age, race/ethnicity, family history of prostate or other cancer, and other pertinent health information will be collected.

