### Treatment Assignment Procedures

#### 3.3.1 Randomization Procedures

Aim 2/3: At the time of consent and enrollment into the study, each participant will be randomly assigned to participate in the intervention arm or the control arm. A randomization scheme will be provided by the study biostatistician.

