### **Study Intervention.**

*Intervention Arm:* Men who are randomized to the intervention arm will be invited to a peer health education session, either in-person or virtually. Eighty-eight of the 176 men will be randomized to this group, and we will host sessions that attract roughly 6-8 men at a session. Our previous experience conducting peer health education sessions found that 6-8 men was an ideal attendance level, as it allowed for interaction and discussion but did not feel overwhelming. Each session will be facilitated by two peer educators, who can share responsibilities and interact with each other. We expect to offer 12-15 sessions, or roughly 1-2 sessions per month. Sessions will be scheduled at various times of the day and days of the week, to accommodate men with varying schedules and commitments. Each peer educator will be compensated for 2 hours of time to run a session from start to finish, being compensated at \$20/hour.

First, the peer educator will introduce the topic of PCA, so that men understand the disease and how it relates to their health. The educator will lead a discussion regarding PCA risk, family history, PCA genetics, considerations of genetic testing, implications of genetic testing on family and self, and financial and ethical considerations. The discussion is meant to be interactive, with men sharing stories and experiences and peer educators answering questions and clarifying facts. All information will be delivered in a culturally appropriate manner by peer educators who are from the community they are serving. Immediately following the discussion, men will complete a post-survey to measure short-term changes knowledge about prostate cancer and genetic testing, thoughts about cancer, in decisional conflict about genetic testing, attitudes toward genetic testing, subjective norms about testing, and intentions to seek genetic testing. We will also get feedback on the peer-led session.

*Control Arm:* After providing informed consent and completing the baseline survey over the telephone or in-person, eighty-eight men will be randomized to this arm and each man will receive an educational booklet. It is expected that materials will be mailed within 24 hours of the

---

telephone call or provided to the participant in person. The information will cover PCA risk, family history, PCA genetics, considerations of genetic testing, implications of genetic testing on family, and financial and insurance considerations.

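### The protocol gives conflicting orders for consent, baseline survey and randomisation, so the baseline SURE score could be taken before assignment in controls and after it in the intervention arm

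*Combined protocol and SAP*

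**What the plan says.** The sequence is described in several places, and they do not agree.

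- **Section 6, Study Randomization and Informed Consent.** "Those who are eligible to participate will be randomized to either the intervention or the control arm". The paragraph next says what each arm will be scheduled for or sent, and only then: "All men who agree to participate will be read a consent statement over the phone or in person and will verbally agree to consent to" take part. The Baseline Survey paragraph follows: "All participants will complete a brief baseline questionnaire over the telephone or in person with the study manager".
- **Section 3.3.1.** "At the time of consent and enrollment into the study, each participant will be randomly assigned". The baseline survey is not placed. The only other detail is that the biostatistician supplies the scheme.
- **Section 6, Control Arm.** "After providing informed consent and completing the baseline survey over the telephone or in-person, eighty-eight men will be randomized to this arm".
- **Section 6, Intervention Arm.** "Men who are randomized to the intervention arm will be invited to a peer health education session, either in-person or virtually". Neither consent nor baseline is mentioned before that step.
- **Section 6, Participant Compensation.** Intervention men are paid for a baseline survey that is linked to the mail.
- **Section 14.3.** The same payment is linked to a baseline survey at the education session.

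Section 9.2 defines the primary analysis as a two-sided t-test on the change in SURE score from baseline to two months, by randomised group. ANCOVA that includes the baseline score is a sensitivity analysis, to be run if baseline imbalance raises concern. Neither concealment of the allocation nor blinding of the person taking the baseline survey is described.

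**The concern.** A man invited to a peer session, or attending one, knows his arm. If his baseline SURE items are answered then, his answers may reflect what he expects from the session, and the person asking may also know the arm. Controls, following their own paragraph, would have answered before assignment. The two baselines would then differ in timing, mode and knowledge of arm. Half of the primary outcome is that baseline.

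A second risk depends on reading the Study Randomization and Informed Consent paragraph literally. If men are assigned and then asked to agree, those who decline leave after randomisation and give no data. It would then be unclear who belongs to the intention-to-treat set. The arms ask for different effort, a group session or a booklet, so declining could differ between them.

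**Working it through.** **1. The sections side by side**

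| Place | Assignment relative to consent | Baseline relative to assignment | Mode of baseline |
|---|---|---|---|
| 3.3.1 (both arms) | same time | not stated | not stated |
| 6, Study Randomization and Informed Consent, then Baseline Survey (both arms) | consent described after assignment; order implied only | described after assignment; order implied only | telephone or in person |
| 6, Control Arm | after consent | baseline first, stated | telephone or in person |
| 6, Intervention Arm | not stated | not stated | not stated |
| 6, Participant Compensation (intervention) | not stated | not stated | mail |
| 14.3 (intervention) | not stated | at the session, so after assignment | at the session |

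Only the Control Arm paragraph states an order in words. No row expressly puts the intervention arm's baseline before assignment, and one row puts it after.

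**2. The plan's own sample size (not in dispute)**

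Inputs from Section 9.3: difference 0.40, SD 0.76, two-sided 5%, 90% power, 75 per arm.
n = 2 × (1.960 + 1.282)² × 0.76² / 0.40² = 75.9, so 76 per arm against the stated 75. Power at 75 per arm is 0.897 by the normal approximation and 0.893 by the exact t-test. Attrition: 150 / 0.85 = 176.5, against the stated 176. The plan's figures reproduce closely.

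**3. How a baseline shift reaches the estimate**

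Estimate = (endpoint − baseline) in the intervention arm, minus the same in controls. If the intervention arm's recorded baseline moves by b because the arm is known, the estimate moves by b in the opposite direction, in full. ANCOVA with baseline coefficient β moves by β × b. With β = 0.5, for example, half the shift remains. Adjustment reduces the shift but does not remove it.

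**4. Size under assumed shifts**

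The documents give no value for b, so 0.05 to 0.20 is an assumption. The SD of change is also assumed, at 0.76. Section 9.3 gives that figure for summary scores, and it carries over to changes if the baseline–endpoint correlation is 0.5, since √(2 × (1 − 0.5)) = 1.
Standard error = 0.76 × √(2/75) = 0.124.

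| b | b / 0.40 | b / SE | Two-sided error rate if there is no true effect | Power for a true 0.40 if b works against it |
|---|---|---|---|---|
| 0 | 0% | 0 | 5% | 89% |
| 0.05 | 12.5% | 0.40 | 6.9% | 80% |
| 0.10 | 25% | 0.81 | 12.6% | 67% |
| 0.20 | 50% | 1.61 | 36% | 36% |

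With SD 0.80 (the value for which 0.40 is exactly half an SD), the error rates are 6.7%, 11.8% and 33.1%. The direction of b is unknown. More participants would not reduce it.

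**5. Refusal after assignment**

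Bias = (fraction of one arm refusing after assignment) × (difference in change score between men who stay and men who refuse). The documents supply neither input. The second must be a difference in change: a stable difference in level cancels. This part is left without a size.

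**The case against.** The strongest reply is that a man's arm is unknown until he is randomised. If future controls complete consent and baseline before a single common randomisation, future intervention men must do so too. The Control Arm paragraph is the only one with an explicit time word, and consent, baseline and assignment in one call would also fit Section 3.3.1. The counts agree: 176 enrolled and 88 assigned to each arm, with no allowance for men lost between assignment and consent. Section 11 also promises a manual of procedures, which may settle the order.

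Much of this stands. If the Control Arm order governs both arms, the problem disappears. But the protocol does not say so, and Section 14.3 points the other way. That sentence concerns payment and could be read as saying when the money is given. Its parallel wording for the endpoint survey, where mode and timing clearly belong to the survey, makes this the less natural reading.

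A reader might go further and infer that the protocol randomises men before consent, so that they accept or refuse knowing their arm. The text does not establish this. The order comes from the sequence of sentences under a joint heading and from the phrase about eligible men, while Section 3.3.1 ties assignment to consent for every participant.

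A reader might also take the recruitment statement, "we will have to screen about 10 times that number, or about 2000 men", as evidence of heavy refusal after assignment. 176 / 2000 = 8.8% is enrolled per screened. It is not broken down, and it can include men who are ineligible, not reached, or unwilling before any assignment. Nor is it stated that the person who screens a man is the one who takes his baseline.

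**Conclusion.** The conflict is in the current text and should be resolved. What is established is that the sections disagree on order and mode, and that none of them expressly protects the intervention arm's baseline from knowledge of the arm. Bias is a possibility that the text permits, not a certainty.

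If baseline is taken after assignment in one arm only, any resulting shift passes one-for-one into the primary estimate, and the conditional ANCOVA does not remove it. Its size rests on assumption: 0.05 to 0.20 units would be 12.5% to 50% of the 0.40 target, with a two-sided error rate of about 6.9% to 36% at 75 per arm and SD of change 0.76. The lower end is small. The upper end would undermine the comparison. Refusal after assignment would additionally blur the intention-to-treat set, but only on the literal reading of the Study Randomization and Informed Consent paragraph, and by an amount the documents cannot give. The sample size is unaffected.

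**What to change.** Reconcile Section 3.3.1, the Study Randomization and Informed Consent, Baseline Survey, Intervention Arm, Control Arm and Participant Compensation paragraphs of Section 6, and Section 14.3 to one sequence for both arms:

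1. Eligibility screen.
2. Verbal consent that describes both arms.
3. Baseline survey completed, by the same mode in both arms.
4. Assignment revealed from a concealed list prepared by the biostatistician; state who holds the list.
5. Session scheduled or booklet issued.

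Count every man assigned at step 4 as randomised: 176 enrolled, about 150 expected for analysis. Record the date and mode of baseline and the date of assignment, so the order can be checked.

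The cost is mainly wording and a concealed list. Section 13.2 has surveys completed on paper and entered later; a completed paper form before step 4 is enough, so data capture need not change. The downsides are small. The arm cannot be disclosed until the baseline survey is finished, and the intervention arm's baseline can no longer be taken at the session or by mail after assignment. Because the endpoint is timed from the session or the mailing, the interval from baseline to endpoint will be longer in the intervention arm by the wait for a session (one or two are planned per month). That interval should be reported by arm.
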